#### **8.1.4. Safety Monitoring Roles**

The site personnel will carefully monitor each patient throughout the study for possible AEs. All AEs will be documented on the eCRF designed specifically for this purpose, and will be followed until either completely resolved or until a stable chronic outcome is determined by the Principal Investigator. SAEs will be reported in accordance with Section 8.1.3.

The Medical Monitor must promptly review all information relevant to the safety of an investigational new product received from any source. The Medical Monitor will also review alert laboratory results in real time and will contact Investigators as needed to ensure that issues are managed in an appropriate manner.

The medical monitor and the Sponsor will review safety data approximately on a quarterly basis, accessed through the EDC system and associated reporting tools, in order to identify potential safety issues/trends that may not be apparent through individual AE reporting. If systematic review identifies a pattern of concern, Sponsor will take steps to address the issues including, but

not limited to, modifying the protocol and/or notifying investigator, authorities and IRB/ECs. Each review will be documented and filed in the Trial Master File.

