### 4.2. General Statistical Methods and Data Handling

#### 4.2.1. General Methods

All output will be incorporated into Portable Document Format (PDF) or Word files, sorted and labeled according to the International Conference on Harmonisation (ICH) recommendations, and formatted to the appropriate page size(s).

A list of tables, figures and listings to be generated, as well as mock shells, are provided in a separate document.

Tabulations will be produced for appropriate demographic, baseline, efficacy and safety parameters. Each table will present all patients combined, regardless of number of doses, unless otherwise specified.

For categorical variables, summary tabulations of the number and percentage within each category (with a category for missing data) of the parameter will be presented.

For continuous variables, the number of non-missing values (n), the mean, median, standard deviation (SD), confidence intervals (CI), minimum and maximum will be presented. Additional statistics may be presented for certain endpoints as described in the sections below.

Time to event data will be summarized using Kaplan-Meier Methodology using 25th, 50th (median), and 75th percentiles with associated 2-sided 95% confidence intervals, as well as percent of censored observations.

If performed, all statistical tests will be two-sided and a difference resulting in a p-value of less than or equal to 0.05 will be described as statistically significant and potentially informative.

All collected data will be presented in patient listings.

The sections below describe the intended analysis of the endpoints. Additional sensitivity analysis may be employed in the event of any unforeseen data anomalies or data issues not known at the time of writing this analysis plan.

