**Unscheduled visit windowing:**

If a patient receives their second dose of study medication at an unscheduled visit that is not  $>3$  weeks after Week 24, the dosing information and all other data collected at that visit will be mapped to the closest nominal visit, based on Rel Day Dose 1, even if data is already available in that visit. All data collected at the time of the second dose will be used for analysis. If data is available in the nominal visit, but was not collected at the unscheduled visit associated with the second dose, the data from the nominal visit will be used. If a patient receives their second dose at an unscheduled visit that is  $> 3$  weeks past Week 24, data from that unscheduled visit will not be used for time to second dose analyses or exploratory efficacy analyses involving two-dose patients.

Data collected at unscheduled visits that are not associated with the second dose will be mapped to the closest scheduled visit, but only if that data is not already available in that visit. Otherwise data will be summarized and presented according to the nominal visit as recorded on the Case Report Form (CRF).

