#### **4.10.2. Laboratory Data**

Clinical laboratory values will be expressed in the international system of units (SI).

The following values will be summarized for each hematology and clinical chemistry laboratory parameter for all patients combined:

1. Baseline (Screening) - Observed
2. Second dose visit (two-dose group only) - Observed and change from baseline
3. Final study visit - Observed and change from baseline

In the event of repeat values, the last non-missing value per study visit will be used.

All laboratory data, including Common Terminology Criteria for Adverse Events (CTCAE) 4.03 grade, will be provided in data listings. See [Appendix A](#) for CTCAE grade definitions.

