#### **4.10.3. Vital Signs, Physical Examination, and Index Knee Assessment**

The following values will be summarized for each vital sign parameter for all patients combined:

1. Baseline - Observed
2. Second dose visit (two-dose group only) - Observed and change from baseline
3. Final study visit - Observed and change from baseline

In the event of repeat values, the last non-missing value per study visit will be used.

Vital sign measurements will be presented for each patient in a data listing.

All clinically significant abnormalities noted in the physical examination will be presented in a data listing.

The following values will be summarized for incidence of inflammation, as determined from the index knee assessment, for all patient combined:

1. Baseline - Observed
2. Second dose visit (two-dose group only) - Observed
3. Final study visit - Observed

For those patients experiencing inflammation, the details of the inflammation (tenderness, swelling, effusion, heat/redness, Baker's cyst) will also be presented. In these tabulations, percentages will be based on those patients who have a non-missing index knee assessment at a given visit.

Index knee assessment as well as index knee aspiration data will be presented in a data listing.

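### The laboratory and vital-sign tables depend on how a recheck is labelled, and no laboratory table counts patients by worst CTCAE grade, so laboratory abnormalities not reported as adverse events may appear only in listings

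*SAP*

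**What the plan says.** - **Repeats.** SAP 4.10.2 (laboratory) and 4.10.3 (vital signs) carry the same sentence: "In the event of repeat values, the last non-missing value per study visit will be used".
- **Rows.** Both sections summarise three points only: baseline, the second-dose visit (two-dose patients) and the final study visit.
- **Unscheduled visits.** Under SAP 4.2.9, data from an unscheduled visit not linked to the second dose "will be mapped to the closest scheduled visit, but only if that data is not already available in that visit". A second dose given at an unscheduled visit is treated differently. If that visit is no more than 3 weeks after Week 24, its data go to the closest nominal visit even if that visit is already filled: "All data collected at the time of the second dose will be used for analysis".
- **Grades.** "All laboratory data, including Common Terminology Criteria for Adverse Events (CTCAE) 4.03 grade, will be provided in data listings". Section 4.10.2 names no table by grade, by shift or by worst value. For vital signs: "Vital sign measurements will be presented for each patient in a data listing".
- **Statistics.** SAP 4.2.1 has the minimum and maximum among the summaries of continuous variables: "the mean, median, standard deviation (SD), confidence intervals (CI), minimum and maximum will be presented".
- **Adverse event route.** Protocol 8.1.1 makes a clinically significant laboratory abnormality an adverse event, and Protocol 8 sends clinically significant safety findings to the adverse event form. SAP 4.10.1 tabulates treatment-emergent events by system organ class, preferred term and maximum severity. Protocol 8.1.4 adds: "The Medical Monitor will also review alert laboratory results in real time".

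**The concern.** The primary objective is the safety of repeat administration, so the laboratory tables are part of the primary evidence. An abnormal first result is one natural reason to repeat a test. If the repeat is filed under the same visit, the abnormal value leaves the summary altogether, including the maximum, where a single outlier shows best. If it is filed as an unscheduled visit, the abnormal value stays. A safety table should not turn on that clerical choice.

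The SAP also sets out CTCAE cut-offs in Appendix A and derives the grades, but tabulates none of them. What remains is the adverse event route, which depends on the investigator's judgement of clinical significance in an open-label study. A value that is normal on recheck is plausibly the one most easily judged not significant. Elsewhere the SAP is more cautious: uncertain onset of an adverse event is resolved by a worst-case rule, a missing relationship is counted as related, and X-ray findings get shift tables.

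**Working it through.** **Tracing the rules for a laboratory value**

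| Case | Rule that applies | Laboratory table |
|---|---|---|
| 1. Abnormal value, repeated under the same visit | 4.10.2, last non-missing value | Abnormal value out, repeat in |
| 2. Abnormal scheduled value, recheck recorded as an unscheduled visit not tied to dose 2 | 4.2.9, visit already has data | Abnormal value stays, recheck out |
| 3. Abnormal value first seen at such an unscheduled visit, closest visit already filled | 4.2.9 | Abnormal value out |
| 4. As case 3, but the closest visit has no laboratory draw | 4.2.9 maps it; 4.10.2 has no row for that visit | Abnormal value out |
| 5. Sample at an unscheduled second-dose visit (not more than 3 weeks after Week 24) | 4.2.9 exception | Used |
| 6. Any of these, judged clinically significant after dosing | Protocol 8 and 8.1.1; SAP 4.10.1 | In the adverse event tables, whatever happens above |

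Cases 1 and 2 can be the same two results with different labels, and the table differs. Section 4.2.9 closes by saying that data are otherwise presented under the visit recorded on the case report form. That does not rescue case 3, because 4.10.2 has no row for unscheduled samples.

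**How long case 4 can last.** Protocol Table 1, footnote 6, has chemistry and hematology at the second-dose visit or, for patients not eligible for a second dose, at the final visit; otherwise they are done at Screening and Week 52. After a second dose at Week 12, the next laboratory row is 52 − 12 = 40 weeks later, with nine scheduled visits between (Weeks 16 to 48). After a second dose at Week 24 it is 52 − 24 = 28 weeks, with six visits between (Weeks 28 to 48).

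**Pre-injection limit.** Table 1 requires the second-dose laboratory tests and vital signs before dosing, and SAP 4.2.10 defines the second-dose baseline as pre-injection. The repeat-value sentence carries no such limit, so a repeat taken after the injection could fill that row.

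**Size.** The plan's sizing figure reproduces: 200 × 0.66 × 0.75 = 99, against a stated 100. The point does not depend on it, but it supplies a denominator: 200 × 0.66 = 132 two-dose patients. SAP section 5 reports more than 90% receiving a second dose, so 200 × 0.90 = 180 is an alternative.

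The documents give no rates, so the following are assumptions for case 1 only. Take 2% to 10% abnormal at a tabulated visit, 50% to 100% of those repeated at the same visit, and 50% to 100% of repeats normal. Patients whose abnormal value leaves the summary, per parameter and visit:

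- 132 patients: 132 × 0.02 × 0.5 × 0.5 = 0.7, up to 132 × 0.10 × 1 × 1 = 13.2.
- 180 patients: 0.9 up to 18.

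If no recheck is a same-visit repeat, the number is 0.

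The effect on the statistics can be seen with 99 assumed values of 5.5 mmol/L and one of 15.0 (Grade 3 for glucose in Appendix A, above 13.9), repeated as 6.0:

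- Mean using the first value: (99 × 5.5 + 15.0)/100 = 5.595; maximum 15.0.
- Mean using the last value: (99 × 5.5 + 6.0)/100 = 5.505; maximum 6.0.

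The mean moves by 0.09 mmol/L. The maximum loses the outlier.

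**The case against.** The strongest reply is that nothing important is lost. A clinically significant abnormality is an adverse event and is tabulated as one, alert results are reviewed as they arrive, and the listings hold every value, first and repeat, with laboratory grades. Protocol 9.4.4 promised only descriptive summaries of value and change, which the SAP delivers. This stands for clinically significant findings. It does not cover a graded value that the investigator did not report, and medical monitoring protects patients without tabulating anything.

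Second, hematology and chemistry go to a central laboratory, so a recheck prompted by a result is plausibly a later sample rather than a same-visit repeat. That would make case 2 more common than case 1 for laboratory data. This is an inference, but a fair one, and it limits how often values are overwritten. It does not touch cases 3 and 4.

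Third, glucose is a weak example of harm. The sponsor's dedicated glucose study looked at 72 hours and 15 days after injection (Protocol 5.2.6). Here chemistry is scheduled before dose 2 and at the final visit, so an acute glucose effect is not sampled on schedule and the repeat rule cannot hide it. This stands; glucose serves above only to show the arithmetic.

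Fourth, the list of tables and the mock shells are in a separate document (SAP 4.2.1). A grade table could be there, but section 4.10.2 does not call for one.

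**Conclusion.** The point holds in a limited form. Laboratory and vital-sign summaries depend on the label given to a recheck. Some unscheduled laboratory samples have no place in the tables, and no laboratory table counts patients by grade. Laboratory abnormalities not reported as adverse events may therefore appear only in listings. CTCAE grading applies to laboratory data alone, so for vital signs only the repeat-value rule is at issue.

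A reader might infer two stronger things, and the documents support neither:

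- *That abnormal results which prompted a recheck reach no safety table.* Case 6 contradicts this for clinically significant findings, and case 5 is a further exception to the unscheduled-visit rule.
- *That the two rules together select values towards normal.* For rechecks they pull in opposite directions: case 1 drops the abnormal value and case 2 keeps it.

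The size cannot be computed from the documents. The ranges above rest on assumed frequencies and show only the mechanism. This is a cheap improvement, not a flaw that invalidates the safety analysis.

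**What to change.** 1. In SAP 4.10.2, add one table of shift from baseline to worst post-baseline CTCAE grade. Use all valid scheduled, repeat and unscheduled values, and exclude samples that the laboratory marks invalid. Show dose 1 to dose 2 and dose 2 to end of study; for one-dose patients, show dose 1 to end of study. Give low and high directions separate rows where Appendix A has both. Appendix A gives the same range for Grades 1 and 2 of low potassium, so state how such a value is graded.
2. In SAP 4.10.2 and 4.10.3, state one repeat-value rule for means and changes that applies alike whether the recheck is filed as a repeat or as an unscheduled visit. Limit it to pre-injection values at the second-dose visit. This part is secondary: where all second-dose-visit values are taken before the injection, as Protocol Table 1 requires, the result at that visit may barely change.

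The cost is SAP wording and one extra table from data already collected and grades already derived. The downside is that a faulty sample which the laboratory has not marked invalid could count as a patient's worst grade.

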#### **4.10.3. Vital Signs, Physical Examination, and Index Knee Assessment**

The following values will be summarized for each vital sign parameter for all patients combined:

1. Baseline - Observed
2. Second dose visit (two-dose group only) - Observed and change from baseline
3. Final study visit - Observed and change from baseline

In the event of repeat values, the last non-missing value per study visit will be used.

Vital sign measurements will be presented for each patient in a data listing.

All clinically significant abnormalities noted in the physical examination will be presented in a data listing.

The following values will be summarized for incidence of inflammation, as determined from the index knee assessment, for all patient combined:

1. Baseline - Observed
2. Second dose visit (two-dose group only) - Observed
3. Final study visit - Observed

For those patients experiencing inflammation, the details of the inflammation (tenderness, swelling, effusion, heat/redness, Baker's cyst) will also be presented. In these tabulations, percentages will be based on those patients who have a non-missing index knee assessment at a given visit.

Index knee assessment as well as index knee aspiration data will be presented in a data listing.

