### 7.9.5. Index Knee Assessment

The index knee assessment will be performed by the designated assessor at the days indicated in Table 1. The index knee will be assessed for tenderness, heat/redness, swelling, effusion, and Baker's cyst. If there is a clinically significant finding outside of the patient's typical disease state at the Screening or Baseline Visit, add to the Medical History. At time points post-baseline, if there are new clinically significant findings outside of the patient's typical disease state or findings that worsen from the patient's baseline condition, record as AEs.

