## Osteonecrosis and Insufficiency Fracture

Osteonecrosis and insufficiency fracture are each measured on a binary scale as absent or present (0=absent, 1=present) and will be adjudicated as follows:

- If Reader 1 and Reader 2 agree (are concordant) on the score of absent or present, then that score is used in the analysis.
- If Reader 1 and Reader 2 do not agree (are discordant) on the score of absent or present, then the X-ray will be read by a third independent radiologist and scored as absent or present. The adjudicated score will agree with either Reader 1 or Reader 2 and that score will be used in the analysis.

Change from baseline to end of study in JSON score will be presented for two-dose patients by patient group (timing of second dose) and for all two-dose patients combined. Any patients whose serial x-rays demonstrate a  $\geq 2$ -point grade increase in JSON will be categorized as indicating Chondrolysis. The frequency and percentage of Chondrolysis will be presented in a summary table for the PPIP and SP separately.

Shift tables of joint space narrowing, subchondral bone changes, osteonecrosis and insufficiency fracture will be presented for two-dose patients, showing shifts from baseline to the end of study by patient group (timing of second dose) and for all two-dose patients combined. These tables will be presented for the PPIP and SP separately.

These X-ray data for all patients, including results for each reader, will be presented in a by patient listing. A separate listing will present baseline Kellgren-Lawrence (K-L) Grade.

After review of X-ray results additional sensitivity analyses may be performed to better understand imaging results.

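### The index-knee inflammation table in SAP 4.10.3 is labelled incidence but shows prevalence, so knees clear at the second dose and inflamed at the final visit cannot be counted from it

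*SAP*

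**What the plan says.** The index knee assessment is one of the safety variables named in SAP 2.5.1, under a primary objective of repeat-dose safety (SAP 1.2.1). SAP 4.10.3 introduces its summary with "The following values will be summarized for incidence of inflammation, as determined from the index knee assessment, for all patient combined". After a baseline row come "Second dose visit (two-dose group only) - Observed" and "Final study visit - Observed". The signs behind any inflammation (tenderness, swelling, effusion, heat or redness, Baker's cyst) are also shown, and "percentages will be based on those patients who have a non-missing index knee assessment at a given visit". The same section adds that "Index knee assessment as well as index knee aspiration data will be presented in a data listing".

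Neighbouring safety variables are linked within patients. Vital signs (4.10.3) and laboratory values (4.10.2) get a change from baseline at the second-dose and final visits. For imaging (4.10.5), "Shift tables of joint space narrowing, subchondral bone changes, osteonecrosis and insufficiency fracture will be presented for two-dose patients".

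Two other parts of the plan bear on this:

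- **Adverse events.** The rule in Protocol 7.9.5 opens "At time points post-baseline, if there are new clinically significant findings outside of the" and goes on to the patient's usual disease state. Its second limb is "findings that worsen from the patient's baseline condition, record as AEs". Protocol 8.1.5 asks that any new or worsened index-knee event, relative to baseline status, be reported. SAP 4.10.1 tabulates index-knee related TEAEs, including periods after the second dose.
- **Baseline.** The knee is examined at Screening and on Day 1 (Protocol Table 1). SAP 4.2.10 takes Day 1, with Screening as fallback. SAP 4.10 takes the screening value for changes in safety variables.

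**The concern.** Incidence means new cases among those previously free of the condition. Three cross-sectional percentages do not give that. A knee that was clear at the second injection and inflamed at the end adds one to the final row, and so does a knee that was inflamed throughout. A knee that cleared subtracts one and can cancel a new case.

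The study exists to describe what a second injection does, and the examined state of the injected joint is one of its safety variables. A steady percentage across the second-dose and final rows would be compatible with no knee changing state and with many changing in both directions. The SAP gives no reason for leaving this variable without a within-patient summary when imaging has one.

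**Working it through.** **1. The plan's own figure.** SAP 4.1 gives 200 enrolled, 66% eligible for a second dose and 75% of those completing. 200 × 0.66 = 132, and 132 × 0.75 = 99, in line with the stated aim of about 100 two-dose completers. I use n = 99 as the paired cohort.

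**2. Who is in each row.**
- On the planning figures: 200 at baseline and 132 at the second-dose visit. The final visit has 99 two-dose completers plus up to 200 − 132 = 68 one-dose patients. The one-dose share is at most 68/167 = 41%.
- As conducted, SAP 5 reports more than 90% receiving two doses and about 10 patients receiving one. Assuming 190 and 10 with 75% completion, the final visit has about 142 + 10 = 152, with a one-dose share of 10/152 = 7%.

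The sets are nested and largely the same people.

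**3. What two percentages say about new cases.** Let S be the number inflamed at the second-dose visit and F the number at the final visit, among n patients seen at both. The number clear at the first and inflamed at the second lies between max(0, F − S) and min(F, n − S). The documents give no rate, so S and F are assumptions:

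| Second-dose visit | Final visit | S | F | New cases possible |
|---|---|---|---|---|
| 10% | 10% | 10 | 10 | 0 to 10 |
| 20% | 20% | 20 | 20 | 0 to 20 |
| 30% | 30% | 30 | 30 | 0 to 30 |
| 20% | 30% | 20 | 30 | 10 to 30 |
| 30% | 20% | 30 | 20 | 0 to 20 |

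A paired table replaces each range with one count.

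**4. Dropout alone can move the percentage.** Take 26 of 132 inflamed at the second-dose visit (19.7%) and let 33 leave with no knee changing state. The final percentage depends on how many leavers were inflamed:
- none: 26/99 = 26.3%
- 7: 19/99 = 19.2%
- 20: 6/99 = 6.1%

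This assumes that leavers have no early-termination knee examination. Protocol 7.4.4 has such visits follow the Week 52 schedule, which includes one, so the real effect should be smaller.

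**5. Tracing one knee through the adverse event rule.** Suppose effusion on Day 1, none at the second-dose visit, and the same effusion at Week 52. It is no worse than baseline, so the second limb of Protocol 7.9.5 is not met. It can be judged usual for that patient, so the first limb need not be met. Nor is it a change from baseline status under 8.1.5. In the planned table it is one affected knee at the final visit, indistinguishable from a knee that never cleared. Only the listing shows the sequence.

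**6. Timing.** Table 1 schedules no knee examination between the second-dose visit and Week 52. The gap is 52 − 12 = 40, 52 − 16 = 36, 52 − 20 = 32 or 52 − 24 = 28 weeks.

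**The case against.** The case for leaving the section alone is substantial.

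- New knee events are meant to be counted in the TEAE tables, which carry onset dates, severity and relationship. For two-dose patients these cover the second dose to 12 weeks later and baseline to Week 52. The summary by dose-timing group also runs from the second dose to Week 52. *This stands for findings that become adverse events.* It does not cover the knee in step 5.
- Under Protocol 7.9.5, clinical significance qualifies new findings, not worsening ones, and 8.1.5 is broader still. *This narrows the gap.* The reference remains baseline, not the second-dose visit.
- Signs are shown separately at each visit, so falling tenderness cannot hide rising effusion in the effusion count. *This stands.* Cancellation is hidden only in the any-inflammation row and within a single sign.
- A shift table misses inflammation that arises and resolves before Week 52, which adverse event reporting can catch. Patients also receive the second dose when it is judged indicated, so shifts from that visit may lean towards improvement. *Both are limits on what the added table can show.*

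A reader might infer that new inflammation after the second injection is invisible in the whole plan. The listing, per-sign counts and TEAE tables show otherwise. A reader might also infer that the three rows describe different patients, but step 2 shows nested sets, with little one-dose mixing as conducted.

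**Conclusion.** The table is mislabelled and cannot yield a count of knees that went from clear at the second-dose visit to inflamed at the final visit. What is missing from the plan's summaries is narrow: signs that returned after clearing, and new signs not judged clinically significant.

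The size is unknown. The ranges in step 3 are algebraic bounds at assumed rates, and their upper ends need extensive turnover in both directions. They show what the table cannot distinguish and are not estimates of harm. It would be wrong to conclude that stable prevalence conceals many new cases, or that the sponsor would read it as no local harm; neither document says so.

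This is a low-cost improvement to a descriptive safety display. It does not affect sample size or any test.

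**What to change.** In SAP 4.10.3:

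1. Keep the by-visit rows, including the final row, so that one-dose patients' final status is not lost. Relabel them *presence (prevalence) of inflammation*.
2. Add, for two-dose patients, paired absent/present shift tables from baseline to the second-dose visit and from the second-dose visit to the final visit. Do this for any inflammation and for each of the five signs, limited to patients examined at both visits.
3. Identify early-termination assessments used as the final visit, since their timing differs from Week 52.
4. State whether baseline is Screening or Day 1 for this variable, and reconcile SAP 4.2.10 with 4.10.
5. Note that the second shift shows status only at one later point and is read alongside the index-knee TEAE tables.

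The cost is six variables × two intervals = 12 small panels from data already collected, with no new visits, examinations or patients.
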